9.2 Safety Run-in Phase

There is no previous experience with SBRT used concurrently with nivolumab plus ipilimumab in this study population. Therefore, to ensure that the combination is safe, the first six patients enrolled will be treated with a combination regimen consisting in nivolumab 3 mg/kg IV combined with ipilimumab 1 mg/kg IV and SBRT within 3 weeks after the initiation of this combination regimen. Safety will be evaluated using standard safety assessments every 21 days for 4 cycles and then every 2 weeks. If 4 out of the first 6 patients experience Grade 3/4 toxicity during the safety run-in observation period (defined as the first 4-cycles, 12 weeks), enrollment will cease and the study will be halted until further safety analysis of the combination regimen can be performed. If less than 4 out of the first 6 patients experience Grade 3/4 toxicities or require steroids, we will proceed with additional accrual with this regimen to complete a total of 15 patients for Stage 1 interim analysis.

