2.1 Study Design

This is a multi-institution, single-arm phase II study to determine the safety and efficacy of SBRT (up to 2 metastatic sites preferentially lung, mediastinum or bone in combination of nivolumab and ipilimumab in patients with metastatic RCC (with a clear-cell component and at least 1 measurable metastatic lesion that is not being irradiated). The primary endpoints are safety and tolerability as well as ORR of the combination of nivolumab plus ipilimumab with SBRT.

The study is planned based on a two-stage design that allows early termination for lack of efficacy. A safety run-in phase will be included comprising the first 6 patients at minimum to ensure that the combination of nivolumab plus ipilimumab and SBRT is safe. Then, we will determine whether the combination of nivolumab plus ipilimumab and SBRT yields a clinically compelling antitumor activity measured as ORR, and evaluate other endpoints including TTP, DOR, PFS, OS and local control of irradiated sites.

Safety Run-in phase

There is no previous experience with SBRT used concurrently with nivolumab and ipilimumab in this study population. **Therefore, to ensure that the combination is safe, the first six patients will be treated and observed for toxicity for 6 weeks after radiation before continuing with further accrual.** Therefore, six patients will be enrolled at the proposed dose of nivolumab and ipilimumab in combination with SBRT. If 4 out of the first 6 patients experience Grade 3/4 toxicity or a lower grade toxicity requiring immune suppressive therapy during the safety run-in observation period (6 weeks after completion of SBRT), enrollment will cease and the study will be halted until further safety analysis of the combination regimen can be performed. If less than 4 out of the first 6 patients experience Grade 3/4 toxicities or require steroids, we will proceed with additional accrual with this regimen.

Toxicity Event: \geq grade 3 adverse event (CTCAE v 4.0) with an attribution of possible, probable, or definite, as well as need for steroids/ immunosuppressive therapy and lower grade toxicity

Efficacy phase:

A minimax Simon two-stage design is planned with the maximum sample size of 25 (including the 6 in the safety run-in phase). A total of 15 patients will be entered in the first

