9.4 Statistical Analyses of Primary Endpoint

Safety analyses will be performed in all treated subjects. Adverse events will be tabulated and presented with frequencies and percentages using NCI CTCAE version 4.0. Safety population consists of all subjects who receive at least one dose of study medication. The ORR will be estimated as the proportion of subjects who achieve a response (CR/PR) assessed by RECIST. The corresponding two-sided 95% exact confidence interval will be calculated assuming a binomial distribution. The efficacy evaluable population includes all subjects who receive at least one dose of study drug, have an adequate baseline disease assessment and at least one post-baseline response assessment.

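### The safety run-in has no definition of an evaluable patient and no replacement rule, so under the literal 4-of-6 count an event-free patient who misses SBRT or the observation window helps release accrual

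*Combined protocol and SAP*

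**What the plan says.** Section 9.2 gives the operative rule. It states that "the first six patients enrolled will be treated with a combination regimen" that includes SBRT within 3 weeks of starting the drugs. The halt condition is "If 4 out of the first 6 patients experience Grade 3/4 toxicity during the safety run-in observation period", with the period "defined as the first 4-cycles, 12 weeks". The release condition begins "If less than 4 out of the first 6 patients experience Grade 3/4 toxicities or require steroids", and accrual then runs on to 15 patients.

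Section 2.1 describes the same run-in differently. Its size is open-ended ("A safety run-in phase will be included comprising the first 6 patients at minimum"). Its intent is that "the first six patients will be treated and observed for toxicity for 6 weeks after radiation before continuing with further accrual". Its events are counted "during the safety run-in observation period (6 weeks after completion of SBRT".

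Section 7 times the first toxicity review from the enrolment of six patients, not from the end of their observation. After the run-in, section 9.3 applies a Bayesian rule to the cumulative event count, with its first printed boundary at 6 events among 7-8 patients.

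No section defines a run-in-evaluable patient in terms of SBRT received, drug doses or length of observation, and none gives a replacement rule. For tumour response, by contrast, section 4.6.9 does say how patients left unassessed because of rapid progression or toxicity are counted: as non-responders, kept in the denominator.

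**The concern.** Sections 2.1 and 9.2 both justify the run-in by the lack of experience with SBRT given concurrently with the two drugs. A patient who never completes SBRT, or who is lost before the window ends, says little about that combination. With the denominator fixed at six enrolled, such a patient with no recorded event makes it easier to stay below 4.

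The situation is foreseeable. SBRT may be given up to 3 weeks after the first drug dose. During a drug delay, section 3.4.3 continues radiation only if it is unlikely to worsen the adverse event. A Grade 2 event that interrupts SBRT without steroids or other immunosuppression need not be a run-in event. Under 2.1 that patient's window never opens, because it runs from completion of SBRT. Under 9.2 the same patient can pass through all 12 weeks without completing SBRT and be counted as event-free.

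At stake is whether accrual beyond the run-in is released on six real tests of the combination or on fewer. For response, counting an unassessed patient as a non-responder is conservative. For toxicity, counting an unobserved patient as event-free errs in the other direction.

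**Working it through.** **Inputs.** Six patients, halt at 4 or more (the release branch is fewer than 4), from 9.2. Bayesian rule from 9.3: Beta(1,2) prior, suspend if the posterior probability that risk exceeds 0.50 is at least 75%, maximum 25 patients. The proportion of run-in patients who leave event-free before completing SBRT or the window is not in the documents, so it is treated as an assumption.

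**The plan's own figures.** The boundary is the smallest k with Pr(risk > 0.5 | Beta(1+k, 2+n-k)) at least 0.75. It reproduces exactly (6 of 7-8, 7 of 9-10, up to 15 of 24-25). Exact stopping probabilities, checked after every patient from 7 to 25, are:

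| True risk | Printed in 9.3 | Exact |
|---|---|---|
| 0.30 | 2.1% | 2.3% |
| 0.40 | 12.8% | 12.3% |
| 0.50 | 38.5% | 37.6% |
| 0.60 | 71.3% | 72.0% |
| 0.65 | 85.3% | 85.6% |
| 0.70 | 94.6% | 94.2% |

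The match holds for monitoring that starts at patient 7 with every patient fully observed. The printed table therefore leaves out the 4-of-6 halt: including it would give 7.7% at risk 0.30. No operating characteristics are stated for the run-in rule itself.

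**Run-in rule, worst case.** With all six informative, P(halt) = P(X ≥ 4), X ~ Bin(6, p). With m patients counted as event-free, X ~ Bin(6-m, p) and the threshold stays at 4. At p = 0.6:

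- m = 0: 15(0.6⁴)(0.4²) + 6(0.6⁵)(0.4) + 0.6⁶ = 0.311 + 0.187 + 0.047 = 0.544
- m = 1: 5(0.6⁴)(0.4) + 0.6⁵ = 0.259 + 0.078 = 0.337
- m = 2: 0.6⁴ = 0.130
- m = 3: only three patients can have an event, so a halt is impossible

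| True risk | m = 0 | m = 1 | m = 2 |
|---|---|---|---|
| 0.5 | 34.4% | 18.8% | 6.3% |
| 0.6 | 54.4% | 33.7% | 13.0% |
| 0.7 | 74.4% | 52.8% | 24.0% |

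**Averaged over an assumed rate.** If each patient independently has probability d of being counted event-free without having been tested, the counted risk is p(1-d) and P(halt) = P(Bin(6, p(1-d)) ≥ 4). At p = 0.6, d = 5% gives a counted risk of 0.57 and 48.2%; d = 10% gives 0.54 and 42.1%. At p = 0.7 the figures are 67.7% and 60.6%. The chance that at least one of the six is such a patient is 1 - 0.95⁶ = 26% or 1 - 0.90⁶ = 47%.

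**With later monitoring added.** Exact recursion through 25 patients, applying the 4-of-6 halt and then the 9.3 boundaries, with one run-in patient counted event-free throughout: the overall halt probability falls from 77% to 65% at risk 0.6, and from 96% to 91% at 0.7.

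**Timing.** If accrual is released at 3 of 6, the count can reach at most 5 by patient 8 (6 needed) and 6 by patient 9 (7 needed). The earliest possible halt is patient 10, and only if all four new patients have events (3 + 4 = 7).

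**The case against.** The strongest answer is that section 2.1 already covers the point. It says the six will be treated and observed after radiation before accrual continues, and that six is a minimum. On a natural reading, accrual waits for six irradiated and observed patients. This shows the intent, but it answers only in part: no trigger is given for a seventh patient, the 2.1 window has no start for a patient who does not complete SBRT, and 9.2 and section 7 both refer to enrolment.

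Three stronger readings are tempting, and the documents do not support them.

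- A reader might infer that the plan scores unobserved patients as non-events. No section says so; it is what the literal count yields when no event has been recorded.
- A reader might blame section 9.4: "Safety population consists of all subjects who receive at least one dose of study medication". That definition serves the adverse event tables and does not set the run-in denominator.
- A reader might suppose that patients who stop because of toxicity are lost. Under the Toxicity Event definition in 2.1, an attributed event of grade 3 or higher, or a lower-grade toxicity needing immunosuppression, counts as an event. Adverse events are also collected for at least 100 days after the last dose (5.6), so stopping the drugs need not end observation. The exposed cases are mainly missing or incomplete SBRT, withdrawal, and death or departure without a qualifying event.

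It also stands that later monitoring, together with the quarterly toxicity reviews in section 7, is a second safeguard. At risk 0.6 the loss from one such patient is about 12 points overall (77% to 65%), against 21 points for the run-in alone. The safeguard is incomplete: it starts after release, and it carries the same uncounted patients forward.

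**Conclusion.** The concern holds as a gap in the run-in definition. The denominator is six enrolled, evaluability and replacement are undefined, and the literal release rule lets an untested, event-free patient count towards continuing.

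The falls of 34% to 19%, 54% to 34% and 74% to 53% at true risks of 0.5, 0.6 and 0.7 are worst cases. They take one such patient as certain and assume that this patient could contribute no event. They should not be read as the expected loss. Under an assumed rate of 5-10%, the run-in halt probability at risk 0.6 falls from 54% to about 48-42%, before the part that later monitoring recovers. That range rests on the assumed rate and on independence between patients. If the investigators in practice apply the intent of 2.1 and wait for six observed patients, the loss disappears, but the text does not require this.

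**What to change.** First reconcile two contradictions, on which any definition depends:

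- the observation window: 6 weeks after completion of SBRT in 2.1, 12 weeks in 9.2;
- the event definition: 2.1 counts attributed events of grade 3 or higher plus lower-grade toxicity needing steroids or immunosuppression, the halt sentence in 9.2 names Grade 3/4 only, and its release sentence adds steroids.

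Which window and which definition apply is for the sponsor to decide.

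Then state in both 2.1 and 9.2: *The run-in decision is made on the first six evaluable patients. A patient is evaluable if a Toxicity Event occurs in the window, or if SBRT and the full window are completed without one. A patient who is not evaluable is replaced in the run-in count by the next patient enrolled, remains in the safety population and, if otherwise eligible, in the efficacy population.*

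In section 7, tie the first toxicity review to completed observation of those six instead of their enrolment.

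The cost is a few sentences and a somewhat longer run-in when a replacement is needed. The total stays at 25, because run-in patients already count within it.

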2.7.3 Permitted Therapy

Subjects are permitted to use topical, ocular, intra-articular, intranasal, and inhalational corticosteroids (with minimal systemic absorption). Physiologic replacement doses of systemic corticosteroids are permitted, up to 10 mg/day prednisone equivalents. A brief course of corticosteroids for prophylaxis (eg, contrast dye allergy) or for treatment of non-autoimmune conditions (eg, delayed-type hypersensitivity reaction caused by contact allergen) is permitted. Concomitant medications are recorded at baseline and throughout the treatment phase of the study in the appropriate section of the case report form (CRF). All medications (prescriptions

or over the counter medications) continued at the start of the study or started during the study and different from the study drug must be documented in the concomitant therapy section of the CRF.

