3.3.5 Treatment delivery technical factors

Treatment will be initiated within three weeks of the initial treatment planning simulation study. Treatment will be delivered with a minimal inter-fraction interval of 36 hours, and no greater than 84 hours between fractions.

Only photon (x-ray) beams with energies greater than or equal to 6MV are allowed. Tumors located within the lungs should be treated with energies of no greater than 10MV, except for specific beams where large soft tissue distances must be traversed to reach target. Dynamic conformal arcs and flattening-filter-free beams are acceptable. All dose calculations should

be performed with tissue heterogeneity corrections.

Image-guided therapy (IGRT) utilizing on-board cone-beam imaging is required for each fraction prior to delivery of treatment. Patients should be aligned to the visible target volume. In cases where soft tissue contrast is poor on CBCT imaging, fiducial markers should be utilized for more accurate setup.

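### Sections 2.1 and 9.2 give the safety run-in different windows and halt events, so the same six patients can mean proceed under one and halt under the other

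*Combined protocol and SAP*

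**What the plan says.** **Window.** Section 2.1 (Safety Run-in phase) says that "the first six patients will be treated and observed for toxicity for 6 weeks after radiation before continuing with further accrual", and it repeats that the period is 6 weeks from the end of SBRT. Section 9.2 gives a different period: "defined as the first 4-cycles, 12 weeks), enrollment will cease and the study will be halted".

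**Halt event.** Section 2.1 halts on the wider event: "If 4 out of the first 6 patients experience Grade 3/4 toxicity or a lower grade toxicity requiring immune suppressive therapy". Its Toxicity Event definition covers grade 3 or higher events with possible, probable or definite attribution, "as well as need for steroids/ immunosuppressive therapy and lower grade toxicity". The 9.2 halt sentence counts Grade 3/4 only: "If 4 out of the first 6 patients experience Grade 3/4 toxicity during the safety run-in observation period".

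**Proceed event.** Both sections use the same sentence: "If less than 4 out of the first 6 patients experience Grade 3/4 toxicities or require steroids, we will proceed with additional accrual".

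**Related text.** The safety endpoint in 9.1 includes corticosteroid need. In 9.3 the prose sets the 50% limit for Grade 3/4 adverse events, but the boundary row is labelled as Grade 3/4 events or steroid needs. Section 7 plans a toxicity review once six patients are enrolled, and quarterly after that.

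**The concern.** Safety is a primary endpoint, and both sections say that nobody has yet given SBRT together with these two drugs in this population. The run-in decides whether more patients are exposed. With two rules and no order of precedence, the sites and the monitoring committee can reach different decisions from the same data and each be following the protocol.

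The window matters most, because there the two sections can give opposite instructions. The event mismatch is secondary: it leaves outcomes for which 9.2 gives no instruction.

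**Working it through.** **The plan's own figures.** The documents give no operating characteristics for the 4-of-6 rule. The nearest figures are in the 9.3 table. With a Beta(1,2) prior and a stop when P(risk > 0.50) is at least 0.75, the printed boundary counts come back (for example 6 of 7-8 patients, posterior 0.91 and 0.83). Exact stopping probabilities from patient 7 to 25 at true risks 0.30, 0.40, 0.50, 0.60, 0.65 and 0.70 are 2.3, 12.3, 37.6, 72.0, 85.6 and 94.2%. The plan prints 2.1, 12.8, 38.5, 71.3, 85.3 and 94.6%, so the two agree within simulation error. The counts depend only on the prior and threshold, not on which event is counted.

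**Where each window ends** (days from first dose, on-schedule dosing)
- SBRT is given between Day 1 and Week 4 Day 1, which is Day 22 (4.3, footnote e). Section 3.3.5 sets the spacing: "Treatment will be delivered with a minimal inter-fraction interval of 36 hours, and no greater than 84 hours between fractions".
- Earliest end of five fractions: Day 1 + 4 × 36 h = Day 7. Latest: Day 22.
- End of 2.1 window: 7 + 42 = Day 49 to 22 + 42 = Day 64.
- End of 9.2 window: 4 × 21 = Day 84, taking the start as first dose.
- Difference: 84 − 64 = 20 days to 84 − 49 = 35 days, or about 3 to 5 weeks.
- Fourth induction dose: Week 10 Day 1 = Day 64. The 2.1 window closes on or before that day, so it does not count toxicity arising after the dose.

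**Case A, window.** Three patients have Grade 3/4 toxicity inside the 2.1 window, a fourth has it in Week 11, and nobody else has an event or needs steroids. Section 2.1 counts 3 and proceeds. Section 9.2 counts 4 and halts.

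**Case B, event.** Three patients have Grade 3/4 toxicity and one has steroid-treated Grade 2 toxicity, all early. Section 2.1 counts 4 and halts. The 9.2 halt sentence counts 3, so there is no halt. The 9.2 proceed sentence counts 4, so accrual is not released. Neither 9.2 rule applies.

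**How often Case A might arise (illustration).** Let *p* be the 12-week Grade 3/4 risk and *f* the share of those events inside the 2.1 window, with no steroid-only events. Every 2.1 halt is then also a 9.2 halt, so

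P(9.2 halts, 2.1 does not) = P(Bin(6, *p*) ≥ 4) − P(Bin(6, *fp*) ≥ 4).

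| *p* | *f* | *fp* | 9.2 halt | 2.1 halt | difference |
|---|---|---|---|---|---|
| 16/47 = 34% | 0.60 | 0.204 | 10.7% | 1.8% | 8.9% |
| 34% | 0.90 | 0.306 | 10.7% | 7.6% | 3.2% |
| 20% | 0.60 | 0.120 | 1.70% | 0.25% | 1.4% |
| 20% | 0.90 | 0.180 | 1.70% | 1.16% | 0.5% |

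The 34% is the related Grade 3-4 rate for this drug dose without SBRT (1.4). It is cumulative and not tied to 12 weeks. The 20% and the values of *f* are assumptions.

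**The case against.** Several points on the other side stand.

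- **The event mismatch releases no patients.** A reader might infer that 9.2 lets accrual continue in Case B. It does not: the shared proceed sentence counts steroids, so accrual stays closed. A review after six patients is already planned in section 7. What is missing is only the formal halt and safety analysis that 2.1 would require.
- **Most of the cohort is past dose 4 by then.** A reader might infer that 2.1 reopens accrual before any toxicity from the fourth dose can be seen. That holds only for the last-enrolled patients. At 2 patients per month, about 15 days apart, when patient six is at Day 49 to 64, patient five is at Day 64 to 79, patient four at Day 79 to 94 and patient three at Day 94 to 109. At least four are then past dose 4, and three or four are past Day 84. Slower run-in enrollment (2.2 expects 3 to 6 months) can shrink the overlap further.
- **The 35-day end is an extreme.** It needs SBRT from Day 1 at exactly 36-hour spacing. Alternate-day treatment ends no earlier than Day 9, which gives 84 − (9 + 42) = 33 days.
- **Large probabilities for the event mismatch are not supported.** They depend on how many patients have steroid-treated lower-grade toxicity only, and the documents give no such share.
- **The rules pause the study; they do not end it.** Continuous Bayesian monitoring follows the run-in.
- **The 9.3 prose may be shorthand,** since its boundary row agrees with the 9.1 endpoint.

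None of this says which window governs. The section 7 review does not either: it is tied to enrollment and sets no window, event or halt count.

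**Conclusion.** The inconsistency is real and can be seen in the text without any assumed rate. In Case A the two sections cannot both be followed. For each patient the 2.1 window closes about 3 to 5 weeks before the 9.2 window. When accrual reopens under 2.1, the unobserved time concerns mainly the patients enrolled last.

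The window conflict is uncommon but not negligible under the stated assumptions: about 3% to 9% of run-ins at 34% risk and about 0.5% to 1.4% at 20%. These figures show scale only, because the documents give neither the timing of events nor a 12-week risk with SBRT.

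The event mismatch is a gap in 9.2, not an opposite instruction. The steroid limb appears in the 2.1 halt, the 2.1 Toxicity Event, the 9.1 endpoint, the 9.2 proceed sentence and the 9.3 row label, so the 9.2 halt sentence and the 9.3 prose are the outliers. The sponsor should correct this; it does not by itself undermine the design.

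**What to change.** 1. **One event.** Use the 2.1 Toxicity Event in both sections: a grade 3 or higher adverse event, or lower-grade toxicity requiring steroids or other immunosuppression, at least possibly related to treatment. It would help to state that steroid use allowed in 2.7.3 does not count, for example: "Physiologic replacement doses of systemic corticosteroids are permitted, up to 10 mg/day prednisone equivalents".
2. **One window.** Twelve weeks from first dose is suggested, because it includes time after dose 4. Using 6 weeks after SBRT in both sections would also remove the conflict.
3. **Complementary rules in both sections.** Four or more of the first six with a Toxicity Event in the window: halt for safety analysis. Fewer than four: proceed.
4. **Section 9.3.** Use the boundary row's event in the prose too, and confirm that the 50% limit was meant for it. The boundary counts do not change.

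**Cost.** Wording in 2.1, 9.2 and 9.3, and no new data. Compared with 2.1, the 12-week window holds accrual 20 to 35 days longer after patient six, about 1 to 2 patients' worth at 2 per month. The shorter window avoids that delay but leaves toxicity after dose 4 outside the run-in. The wider event will trigger a formal halt more often than Grade 3/4 alone.

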5.1 Definition and Grade

Adverse Events will be reported as indicated by the appropriate following table (see below). An adverse event is defined as any untoward or unfavorable medical occurrence in a human research study participant, including any abnormal sign (for example, abnormal physical exam, imaging finding or clinically significant laboratory finding), symptom, clinical event, or disease, temporarily associated with the subject's participation in the research, whether or not it is considered related to the subject's participation in the research.

Adverse events encompass clinical, physical and psychological harms. Adverse events occur most commonly in the context of biomedical research, although on occasion, they can occur in the context of social and behavioral research. Adverse events may be expected or unexpected.

Acute Adverse Events

Adverse events occurring in the time period from the signing of the informed consent through 100 days post treatment will be considered acute adverse events.

Severity

Adverse events will be graded by a numerical score according to the defined NCI Common Terminology Criteria for Adverse Events (NCI CTCAE version 4) and version number specified in the protocol. Adverse events not specifically defined in the NCI CTCAE will be scored on the Adverse Event log according to the general guidelines provided by the NCI CTCAE and as outlined below.

- Grade 1: Mild
- Grade 2: Moderate
- Grade 3: Severe or medically significant but not immediately life threatening
- Grade 4: Life threatening consequences
- Grade 5: Death related to the adverse event

Serious Adverse Events

ICH Guideline E2A and the UTSW IRB define serious adverse events as those events, occurring at any dose, which meets any of the following criteria:

- Results in death
- Immediately life-threatening
- Results in inpatient hospitalization ^{1,2} or prolongation of existing hospitalization
- Results in persistent or significant disability/incapacity
- Results in a congenital anomaly/birth defect
- Based upon appropriate medical judgment, may jeopardize the subject's health and may require medical or surgical intervention to prevent one of the other outcomes listed in this definition.

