9.1 Study Design

This is a multi-institution, open-label, single-arm Phase II study to determine the safety and efficacy of SBRT followed by nivolumab in combination with ipilimumab in patients with metastatic RCC. The primary endpoints of safety evaluated by the level of G3/4 treatment related adverse events and the need for corticosteroids in this patient population and ORR assessed by RECIST criteria. Secondary endpoints include TTP, DOR, PFS, OS and local control of irradiated lesion. Simon's minimax two-stage design will be used to allow for early termination of the study if addition of SBRT to nivolumab in combination with ipilimumab is unlikely to be promising. A safety run-in phase will be included in the first 6 patients, and safety will be monitored continuously after this safety run-in phase using a Bayesian posterior probability approach.

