Early Stopping Guidelines for Safety: The safety profile of the combination of SBRT with dual immune checkpoint inhibition using nivolumab and ipilimumab is not yet established, and therefore we will conduct continuous toxicity monitoring after safety run-in to ensure this combination is safe. If the risk of Grade 3/4 adverse events convincingly exceeds 50%, a threshold we are comfortable given the potential benefit of the regimen as well as our experience in managing the side effects in this patient population, we will temporarily halt the study and carefully review the available data at that point in order to suggest potential modification of the combination regimen. Specifically, a Bayesian toxicity monitoring rule will suggest suspending enrollment if the posterior probability of risk being larger than 0.50 is 75% or higher. The prior for this monitoring rule is beta (1, 2), representing the risk of DLT has mean of 33% and there is 90% probability that this risk is between 2.5% and 78%. The stopping rules for safety and the operating characteristics based on 5000 simulations are as below.

No. patients experiencing G3/4 AE/steroid needs	6	7	8	9	10	11	12	13	14	15
	Out of	7-8	9-10	11-12	13-14	15-16	17	18-19	20-21	22-23
True risk of AE				Prob. declaring regimen too toxic				Avg. sample size		
0.30				2.1%				24.7		
0.40				12.8%				23.3		
0.50				38.5%				20.1		
0.60				71.3%				15.6		
0.65				85.3%				13.2		
0.70				94.6%				10.9		

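### The safety run-in halting rule differs between Sections 2.1 and 9.2 in the event counted and the observation window, and the two branches in Section 9.2 leave a gap

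*Combined protocol and SAP*

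**What the plan says.** **Section 9.2.** The halt applies if 4 of the first 6 patients "experience Grade 3/4 toxicity during the safety run-in observation period (defined as the first 4-cycles, 12 weeks"). The next sentence reads: "If less than 4 out of the first 6 patients experience Grade 3/4 toxicities or require steroids, we will proceed with additional accrual".

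**Section 2.1.** The halt sentence counts Grade 3/4 toxicity or "a lower grade toxicity requiring immune suppressive therapy during the safety run-in observation period (6 weeks after completion of SBRT"). The same section says that "the first six patients will be treated and observed for toxicity for 6 weeks after radiation before continuing with further accrual". Its proceed sentence has the same condition as the one in Section 9.2. A separate toxicity-event line counts events of at least "grade 3 adverse event (CTCAE v 4.0) with an attribution of possible, probable, or definite, as well as need for steroids/ immunosuppressive therapy".

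**Section 9.1.** The safety endpoint is "the level of G3/4 treatment related adverse events and the need for corticosteroids in this patient population".

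**Section 9.3, early stopping guidelines.** The text begins "If the risk of Grade 3/4 adverse events convincingly exceeds 50"%, while the header of the boundary table counts Grade 3/4 events together with steroid needs. This monitoring is said to start after the run-in.

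**The concern.** Both sections name the same safety run-in observation period and the same 6 patients, but they do not give the same rule.

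- **Event.** A lower-grade toxicity treated with immune suppression counts towards the halt in Section 2.1 and not in Section 9.2. Within Section 9.2 the halt branch counts one event and the proceed branch a wider one, so they are not complements. Section 9.3 has the same split between its text and its table header.
- **Window.** Section 2.1 counts from the end of SBRT and Section 9.2 counts 12 weeks. Events around and after the fourth combined dose may count under one section only.
- **Grade and attribution (lesser).** The toxicity-event line in Section 2.1 has no upper grade limit and requires at least possible attribution. The halt sentences say Grade 3/4 and name no attribution. Section 5.1 lists "Grade 5: Death related to the adverse event", so a related death meets the definition but, read literally, not the halt count.

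The run-in is the gate before further accrual of a combination that the protocol says has not been given concurrently in this population. Two sites have to apply it in the same way.

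**Working it through.** **1. The plan's own safety figures.** The Section 9.3 rule suspends enrolment if the posterior probability that the risk exceeds 0.50 is at least 0.75, with a beta(1, 2) prior. The boundary is the smallest x with P(Beta(1+x, 2+n−x) > 0.5) ≥ 0.75. This gives 6 of 7–8, 7 of 9–10, 8 of 11–12, 9 of 13–14, 10 of 15–16, 11 of 17, 12 of 18–19, 13 of 20–21 and 14 of 22–23. All nine pairs legible in the table agree. The rule gives 15 for 24–25. An exact recursion over patients 7 to 25 gives:

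| True risk | 0.30 | 0.40 | 0.50 | 0.60 | 0.65 | 0.70 |
|---|---|---|---|---|---|---|
| Printed, % | 2.1 | 12.8 | 38.5 | 71.3 | 85.3 | 94.6 |
| Exact, % | 2.3 | 12.2 | 37.6 | 72.0 | 85.6 | 94.2 |
| Printed average N | 24.7 | 23.3 | 20.1 | 15.6 | 13.2 | 10.9 |
| Exact average N | 24.7 | 23.4 | 20.2 | 15.5 | 13.1 | 11.0 |

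The differences are within the error of 5000 simulations. The table is right for the Bayesian rule from patient 7.

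**2. The two run-in rules side by side.**

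| | Section 2.1 | Section 9.2 |
|---|---|---|
| Halt at 4 of 6 | Grade 3/4, or lower grade needing immune suppression | Grade 3/4 only |
| Proceed if fewer than 4 of 6 | Grade 3/4 or steroids | Grade 3/4 or steroids |
| Window | 6 weeks after SBRT ends | 12 weeks |

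Take three Grade 3/4 cases and one lower-grade steroid case. Section 2.1 counts four and halts. Section 9.2 counts three for the halt, so there is no halt, and four for the proceed condition, so there is no permission to proceed.

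**3. How often Section 9.2 gives neither instruction.** Let p be the Grade 3/4 risk and s the risk of lower-grade, steroid-only toxicity. Use one common window and read 4 of 6 as 4 or more. Then

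gap = P(Bin(6, p+s) ≥ 4) − P(Bin(6, p) ≥ 4).

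Section 1.4 gives 16/47 = 34% for related Grade 3–4 events with these drug doses without SBRT. The documents give no value for s, so it is an assumed range; p = 0.20 is an assumed lower case. Differences are taken before rounding.

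| s | 0.05 | 0.10 | 0.20 | 0.30 |
|---|---|---|---|---|
| p = 16/47: Section 2.1 halts, % | 16.6 | 24.0 | 42.2 | 62.8 |
| p = 16/47: Section 9.2 halts, % | 10.7 | 10.7 | 10.7 | 10.7 |
| p = 16/47: gap, % | 5.9 | 13.2 | 31.5 | 52.0 |
| p = 0.20: Section 2.1 halts, % | 3.8 | 7.0 | 17.9 | 34.4 |
| p = 0.20: Section 9.2 halts, % | 1.7 | 1.7 | 1.7 | 1.7 |
| p = 0.20: gap, % | 2.1 | 5.4 | 16.2 | 32.7 |

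**4. Window.** SBRT falls between Day 1 and Week 4 Day 1, which is Day 22 (Section 4.3, footnote e). There are five fractions, at least 36 hours apart (Section 3.3.5).

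- Earliest end of SBRT: Day 1 + 4 × 36 h = Day 7. The Section 2.1 window then closes on Day 7 + 42 = Day 49.
- Latest end: Day 22. The window then closes on Day 22 + 42 = Day 64, the scheduled day of the fourth combined dose (Week 10 Day 1, Section 4.3).
- Section 9.2: 12 × 7 = Day 84.
- Difference: 84 − 64 = 20 days to 84 − 49 = 35 days.

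The Section 9.2 window also equates four cycles with 12 weeks, whereas Table 5 in Section 3.2 sets each of cycles 1 and 2 at 6 weeks.

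**5. The window difference in patients.** Section 9.3 expects 2 patients per month: 20 × 2/30.44 = 1.3 and 35 × 2/30.44 = 2.3. Section 2.2 expects about 18 further months for the efficacy phase; with 25 − 6 = 19 patients that is 1.06 per month, giving 0.7 to 1.2 patients.

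**The case against.** The strongest reply is that the proceed condition is the same in both sections. In the example with three Grade 3/4 cases and one steroid case it fails in both, so neither section authorises further accrual. That stands. A reader might infer from the table in step 3 that up to half of run-ins would lead to accrual that Section 2.1 forbids. The documents do not support this: the gap is the chance that Section 9.2 is silent.

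The inputs are also soft, and this stands too. The steroid-only risk is assumed and drives the result. The 34% comes from an expanded cohort with mature data and no stated 6- or 12-week limit, so it may be high for a run-in.

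On grade and attribution, Sections 2.1 and 9.1 together suggest the intended composite. Deaths are SAEs, reported to the DSMC within 5 business days (Section 5.3) and reviewed on receipt by its chair, who can act at once (Section 5.3.2). A reader might infer that a related death would escape review; it would not. The wording still differs, but this is the lesser part of the point.

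A reader might also infer that the Section 9.3 table misstates the trial's safety characteristics because it leaves out the run-in halt. Sections 9.1 and 9.3 both place the Bayesian rule after the run-in, the table starts at 7 patients, and its figures reproduce. That is not a defect.

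None of these replies removes the different halt events or the different windows.

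**Conclusion.** The run-in rule is contradictory as written and should be reconciled. The event conflict lies between Sections 2.1 and 9.2, inside Section 9.2, and between text and table header in Section 9.3. The window conflict is between sections only; no section gives two run-in windows.

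The silence in Section 9.2 has a chance of 5.9% to 52.0% with Grade 3/4 risk 34%, and 2.1% to 32.7% with 20%, for an assumed steroid-only risk of 0.05 to 0.30, independent patients and a common window. The windows differ by 20 to 35 days if dosing and SBRT run to schedule. Accrual could reopen that much earlier under Section 2.1, for about 0.7 to 1.2 patients at the pace implied by Section 2.2 or 1.3 to 2.3 at the Section 9.3 rate. That the passages conflict rests on the text alone and needs none of these assumptions.

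**What to change.** Reconcile Sections 2.1, 9.2 and 9.3 to:

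- one event definition, stating the grade range (including whether Grade 5 counts), the attribution required, and whether steroid or other immunosuppressive need counts;
- one observation window, with its start and end stated and the cycle wording aligned with Section 3.2;
- two complementary branches on that one event: 4 or more of 6 halts, fewer than 4 proceeds.

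Which event and which window to adopt is the sponsor's clinical decision.

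Keep the Section 9.3 boundaries and figures. They depend on the prior, the threshold and the event risk, so settling the event definition changes the table header or text but needs no recalculation. A note that the table excludes the run-in halt is optional. The cost is a wording amendment in three sections.
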